#### **4.4.2 Integrity threats**

This section describes threats concerning unauthorised modification of information and threats to the information's accuracy, correctness, and completeness. If these data were meant to be used for changes in treatment or medication for the patient, the consequence of wrong information could, in worst case, be very serious. But that is not the purpose of the information in this service. The stored data can be checked by the users themselves, and in in case of strange values, the patient should be called-in for a thorough control by the clinicians.

Most of the integrity threats are among those which were analysed as *low* risk for the users, but as *medium* risk for the service and service provider's reputation, and the users' trust in and motivation to use the service. In all cases, the risk is considered acceptable. These are the threats:

**Threats i1-i4** are related to possible modification of data stored in the servers, either in the Qualcomm backend or in the SENACA servers. Modification could be caused, accidentally or deliberately, by administrators or operators in the operating environment, or by external attackers.

Threats i5, i6, i7 and i10 refer to possible modification of data during transfer, either in the bluetooth transfer in the patient's home (i10), in the mobile network between the hub in the patient's home and the Qualcomm backend (i6), or in internet between Qualcomm backend and SENACA servers (i5). The modifications could be caused by deliberate attacks to the transfer medium, or be caused by software errors (i7).

**Threats i8 and i12** – the possibility that unauthorized persons can log in to the user's account on the web site (**i8**) or via the mobile application (**i12**) and modify the user's information. Authentication mechanisms and password policy for the web interface, seem too weak. Authentication mechanisms for the mobile app is unknown at this point. – Even if these risks can be acceptable for the use in this project, it is strongly recommended to improve the authentication mechanism, as discussed for threat c6 above.

The last integrity threat (i11) has *low* risk level. This threat refers to the possibility that fake/false values are registered for the user because unauthorized persons, e.g. children, "play" with the monitoring equipment. The likelihood may be *moderate*; it depends on who are around and can get hold of the monitoring devices. There are also other uncertainties/questions related to this:

- Will measurements be transferred immediately ("always on")?
- Is it possible for the user to delete their own registrations, e.g. if they discover a false registration?
- Is it possible for the user to insert comments to their own registrations?

The consequence is, however, considered *small* for the patient: data and information can be checked, and it will not be used for change of treatment or medication.

### 4.4.3 Availability threats

This section describes threats concerning information being accessible and usable upon demand by authorized users.

One of the seven availability threats have got *medium* risk level:

**Threat a3** – the possibility that users cannot log in to their web account because of problems with their own private devices (PC, tablet, mobile phone). This may very well happen, the likelihood is set to *moderate*, but it also depends on the users' computer literacy. The consequence is considered *moderate*, mainly because the users may be demotivated if they do not get help to solve such problems. This is more of a private problem for each user, and the risk is considered acceptable.

The rest of the availability threats are among those which were analysed as *low* risk for the users, but as *medium* risk for the service and service provider's reputation, and the users' trust in and motivation to use the service. It depends how long these types of problem last. In all cases, the risk is considered acceptable. These are the threats:

**Threats a1 and a2** – the possibility that users cannot log in to their web account because of problems with the SENACA servers (a1) or because of network problems (a2). The likelihood is set to *low*: We assume that the service providers (Qualcomm, SENACA) are professional organisations with stable systems and quick fix of problems, and the network connections, both mobile network and internet, are also experienced as stable (when existing). As for threat a3 above, the consequence is considered *moderate* for the patient. The consequence is worse (*severe*) for the service provider.

**Threats a4-a7** refer to the problem that monitoring data from the user are not being transferred to the servers. This can be caused by different types of server problems (**a4**), network problems at any level (**a5**), problems at the local access point (hub/aggregator) in the patient's home

(**a6**), or problems with the monitoring equipment itself (**a7**). The likelihood is considered *low* in all cases. Regarding the monitoring devices and the hub, we assume this is a stable and well tested technology. The consequence is considered *small* for the patient, but worse (*severe*) for the service and service provider.

### 4.5 Recommended risk treatment

There are basically four different approaches to handle a risk:

- 1. Accept the risk, in accordance with the organisation's security policy. This approach is usually applied for the risks with an acceptable risk level. *It is worth remembering that accepting the risk does not mean accepting the unwanted incident indicated by the threat.*
- 2. **Reduce** the risk to an acceptable level. Since the risk is a product of likelihood and consequence, this means to reduce the likelihood, the consequence, or both. It is often difficult to reduce the consequence of a threat, so the focus should first of all be on reduction of the likelihood.
- 3. **Avoid** the risk, i.e. try not to be exposed to the risk, not do the things that could lead to the risk.
- 4. **Transfer** the risk to a third party (e.g. an insurance company)

In our analysis we mainly stick to strategies 1 and 2 above and recommend security measures that can *reduce risks*. Risk reduction should be subject to a cost/benefit analysis. Some measures can reduce the risk level for several threats at the same time, and simple and cost-effective measures that can reduce even an acceptable risk, should preferably be implemented.

As can be seen from the analysis in section 4.4, no threats were assessed to have unacceptable risk. Three threats were analysed to have *medium* risk, in addition to a large number of threats which were analysed as *low* risk for the users, but as *medium* risk for the service: its reputation, and the users' trust in and motivation to use the service.

**Threat c6** is the threat closest to not being accepted: The authentication mechanism is password only for login to the user's account (web site). It makes it too easy for unauthorized persons to log in and read sensitive information for that patient. In addition, the web client allows username and password to be stored/remembered. – For this limited project, however, the risk for unauthorized access has been accepted, based on the thought that no one will use this opportunity to log into the user's web-account, no one is really interested in reading these values.

According to Norwegian regulations in Code of conduct for information security, authentication for access to health information via web sites requires use of personal qualified certificate, i.e. security level 4 – or another solution "that based on a risk assessment is considered good enough". For this service we would strongly recommend at least security level

<sup>18 The Norwegian Directorate of eHealth (NDE): Code of Conduct for information security in the healthcare and care services. https://ehelse.no/personvern-og-informasjonssikkerhet/norm-for-informasjonssikkerhet/documents-in-english

3 for access to the user's account, e.g. a one-time password sent via SMS, in addition to username and password.

Acceptable threats with *medium* risk could preferably be treated, and several of the proposed measures will also help to keep a *low* risk on the remaining threats.

The table below gives an overview of possible security measures and indicates the threats which can have the risk reduced by these measures. These measures will then contribute to reduction of the total risk for the system.

Security measures	Related threats
Security training and privacy awareness:	
Keep login credentials (password, PIN) secret	c6, c8, i8, i12
Training/education in use of the service	а3, а5

 
Check the data stored on the SENACA servers (Is it the same as registered by the monitoring devices?)
 
	i1, i2, i3, i4, i5, i6, i7, i8, i11

 
Keep the monitoring devices away from children or other persons who want to "play"/tamper with it
 
	i11
Routines and procedures:	

 
Data processing agreement between UNN and SENACA
 
	c1, c2, i1, i2, i3
Define requirements for password strength	c6, i8

 
Notify users about known unavailability periods
 
	a1, a4, a6
Helpdesk or contact information for support	a1, a2, a3, a7
Software and configuration:	

 
Remove possibility to store/remember login credentials for web account
 
	c6, i8

 
Strengthen the authentication mechanism, e.g. by use of an additional one-time password
 
	c6, c8, i8, i12

 
Possibility for users to comment on registrations from monitoring equipment
 
	c11

#### Table 15: Recommended security measures

In addition, some technical security measures are already built in to the system (see chapter 4.2 and Annex 13):

- User data and medical data stored in different databases.
- Encrypted transfer of data. End-to-end encryption between Qualcomm hub in patient's home and the Qualcomm backend (AES 128 bits)
- Qualcomm backend system transfers observation data to the SENACA servers using Internet HTTPS SSL/TLS.
- SSL/TLS encryption (HTTPS) for web access to stored data
- Remote update of hub software

# 4.6 Conclusion

This report documents the risk assessment of privacy and information security aspects of the Norwegian field-test of the EU-funded project USECARE. The risk assessment was conducted in the November and December 2015 and January 2016.

A total of 29 possible threats were identified. These are listed in the threat table in Annex 14. The result of the analysis (chapter 4.4) shows that no threats were assessed to have unacceptable risk. Three threats were analysed to have *medium* risk, in addition to a large number of threats which were analysed as *low* risk for the users, but as *medium* risk for the service: its reputation, and the users' trust in and motivation to use the service.

Regarding the confidentiality aspect, there are two places where the person identifiable health information (i.e. sensitive information) can be revealed:

- By logging in via a user's account threats c6 (web) and c8 (mobile app)
- At the SENACA servers, where administrators and operators (threat c1) and external attackers (threats c2 and c3) can access both DB Users and DB data.

Threat c6 is the threat closest to not being accepted (see also chapter 5).

Some necessary and useful security measures are proposed in section 4.5, also measures against threats which have an acceptable risk level. By reducing risk for threats which are individually acceptable, the total risk level for the system will be reduced. It is therefore recommended that as many as possible of the proposed measures are being implemented.

# 6 Annexes

#### 6.1 Annex 1 – Additional information on measurements

#### Part I – preliminary studies: usability

Usability of the enhanced SENACA prototype will be evaluated during the implementation in view of user's expected perceived usability and user's experienced perceived usability (see Figure 3). Both will be assessed using the three subscales of the TAM measuring perceived usefulness (PU), perceived ease of use (PEOU) and intention to use at the three time points  $(T_1-T_3)$  (see annex 2a). Furthermore the items of the PSSUQ will be applied (see annex 2b). The TAM is considered a valid and robust model (45). In sum, it consists of a 9-item instrument evaluating four statements on the main determinants of intention to use (PU and PEOU) and one on the planned behaviour respectively the intention to use (IU). While statements on perceived ease of use refer more to the aspect of effortlessness in using ICT applications, statements on perceived usefulness refer rather to perceived benefits gained by the use of technology (see theoretical notes in background section). All subscales are rated on a 7-point Likert-scale (1 = 'extremely unlikely' to 7 = 'extremely likely') (see annex 2a). The TAM measures are brief and easy to use and have good reliability (Cronbach's alpha ranging from 0.82 to 0.98) and good convergent validity (> 0.6) (44,52). The wording of the items will slightly be modified in order to fit the setting of USECARE AAL. Two separate versions will be developed to apply to the pre- and post-implementation periods. In addition, items from Technology Readiness Index will be included to predict technology acceptance or rather perceived ease of use and perceived usefulness on the individual level (25,53,54) (see annex 2c).

The usability parameters will also include the percentage of approached potential users not willing to participate, the attrition rate (number of participants discontinuing with the program during the intervention period), the participants' performance (e.g. completion of self-management tasks) and the percentage of days / households without malfunctioning of the system (devices and website) (see annex 6).

# Part II – pre-experimental design: Quality of life (QoL), health-related behaviour and clinical parameters

A main study parameter is **QoL**, which will be assessed using the EQ-5D (the EuroQol 5dimension inventory) as a generic standardised measure of health status with low respondent burden that provides a cognitively simple, generic measure of health for clinical and economic appraisal (55). The EQ-5D system consists of a self-classifier descriptive system with five dimensions (mobility, self-care, usual activities, pain / discomfort, and anxiety / depression), with each dimension described at five response levels, roughly corresponding to having no, slight, moderate, severe, and extreme problems. The EQ-5D-5L also includes a vertical visual analogue scale (VAS) to enable respondents to provide a self-rating of his or her own health (endpoints with "0" labelled "worst imaginable health" and "100" labelled "best imaginable health"). Although the EQ-5D-5L has been primarily designed as pen-and-paper self-complete instrument, it is available in alternative formats and modes of administration, i.e. for tablet, web or telephone. The EQ-5D-5L and the EQ-5D VAS will be administered at baseline, after 50 days, and along with the final clinical assessment through the web-site interface. Participants will have the option to use the EQ-5D-5L biweekly for voluntary self-monitoring of their quality of life.

# 6.2 Annex 2a – Technology Acceptance Model (TAM)

Please indicate your level of agreement with each of the following statements using the scale provided below.

Remember to **select a single option** for each statement.

-3	-2	-1	0		+1		+2		+2 +3	
Totally disagree	Disagree	Slightly disagree	Neither agree nor disagree	Slightly agree			Agree		To ag	tally jree
1. My inter understandab	action with	SENACA was	clear and	-3	-2	-1	0	+1	+2	+3
2. Interacting effort	with SENACA of	did not require a	a lot of mental	-3	-2 □	-1	0	+1	+2	+3
3. I found SENACA easy to use					-2 □	-1	0	+1	+2	+3
4. I found it easy to get SENACA to do what I wanted it to do					-2 □	-1	0	+1	+2	+3
5. Using S monitoring my	ENACA impro	oved my per	formance in	-3	-2 □	-1	0	+1	+2	+3
6. Using SI increased my	ENACA in he productivity	alth monitorin	g processes	-3	-2 □	-1	0	+1	+2	+3
7. Using SENACA enhanced my effectiveness in monitoring my health					-2 □	-1	0	+1	+2	+3
8. I found SENACA to be useful to monitor my health				-3 □	-2	-1	0	+1	+2	+3
9. Given that intend to use	I had access t it in the future	o SENACA aft	er the study I	-3	-2	-1	0	+1	+2	+3

# 6.3 Annex 2b – Post-Study System Usability Questionnaire (PSSUQ)

Please indicate your level of agreement with each of the following statements using the scale provided below. Remember to **select a single option** for each statement.

1.	Overall, I am satisfied with the system	-3	-2 □	-1	0	+1	+2	+3
2.	Overall, I am satisfied with how easy it was to use the system	-3	-2 □	-1 □	0	+1	+2 □	+3
3.	It is simple to use the system	-3	-2	-1	0	+1	+2	+3
4.	I can effectively manage my health by using the system	-3	-2	-1	0	+1	+2	+3
5.	I am able to manage my health quickly using the system	-3	-2	-1 □	0	+1	+2	+3
6.	I am able to efficiently manage my health using the system	-3	-2	-1	0	+1	+2	+3
7.	I feel comfortable using the system	-3	-2	-1	0	+1	+2	+3
8.	It was easy to learn to use the system	-3	-2 □	-1	0	+1	+2	+3
9.	The system gave error messages that clearly told me how to fix problems	-3	-2 □	-1	0	+1	+2 □	+3
10.	Whenever I made a mistake using the system, I could recover easily and quickly	-3 □	-2 □	-1 □	0	+1	+2	+3
11.	The information provided for the system is easy to understand	-3	-2 □	-1	0	+1	+2	+3
12.	The information provided with the system (online help, documentation) is clear	-3	-2 □	-1	0	+1	+2	+3
13.	It is easy to find the information I need	-3	-2 □	-1	0	+1	+2	+3
14.	The information is effective in helping me managing my health.	-3	-2	-1 □	0	+1	+2	+3
15.	The system has all the functions and capabilities I expect it to have	-3	-2 □	-1	0	+1	+2	+3
16.	I like using the interface of the system Note: The interface includes those items that you use to interact with SENACA such as the screens, graphs and language.	-3	-2	-1	0	+1	+2	+3

17. The organization of information on the system's screens is clear	-3	-2	-1	0	+1	+2	+3
18. The interface of the system is pleasant	-3	-2	-1	0	+1	+2 □	+3

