#### 2.2.8 Data analysis

Explorative and descriptive data analyses will mainly be performed in this field-test study with a relatively small sample size.

First, descriptive analysis on usability will give a general overview of how users, both informal carers and patients, view SENACA before having used it. The findings will be compared with perceived usability after having experienced it for the whole intervention period (up to day 100). This will provide insights on practical implications on the design and introduction of SENACA. A qualitative analysis on break-offs and non-response further completes the findings by exploring the barriers and drivers of usage. In addition to that, the usage of the several components of SENACA will be compared regarding frequency and intensity to explore which aspects are more or less accepted by the user groups.

In a second step, the clinical and behavioural parameters and quality of life will be screened at baseline measurement. This initial description gives further insights into the characteristics of the sample. Changes in parameters over time will be explored to gain insight into the functionality of SENACA.

Overall, mean values will be compared on the basis of non-parametric tests to identify significant differences between groups. Even though the study does not meet the requirements of an experimental design, the ex-ante and ex post measurement allows monitoring changes of the observed variables. Bias due to non-observable errors may be possible.

Data from qualitative study parts (i.e. interview transcripts, content from open-ended questions or user forums) will be coded applying thematic analysis (Bradley, Curry & Devers, 2007) in order to categorize the data as well as to identify patterns leading to a nuanced evaluation of the usability of SENACA from a technological, educational and behaviour perspective. The qualitative analysis will be guided by taxonomies and frameworks on the subject of matter to be used as sensitizing concepts, for instance Michie et al. (2013) or Greenhalgh et al.(2015). Computer-aided qualitative data analysis (most likely MaxQDA®) will be used for coding and synthesising the findings.

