#### 3.2.5 Tasks do be done during the test period

We told the test users to use the system and perform tasks on a regular basis. Registering of personal data, management of the user account (user name and password) and configuring of the medical devices had already been done by the project partners (EMN and UNN). These tasks have not been tested by the test users and this is something that also will be done by the project members when we hand out the systems to the patients and the informal caregivers.

We invited the test users to use the medical devices, to check the result in the SENACA website and to navigate through the system and perform tasks. After having logged in to the SENACA website for the first time, the user could perform the following tasks:

- 1. Nutrition: You have to answer a questionnaire regarding nutrition, health status, activities etc.
- 2. Choose 3 specific items from a list of nutrition items you want to monitor. Register what you have been eating on daily basis. Check your daily and weekly statistics.
- 3. Activity: Check the list of activities and exercises to be performed.
- 4. Register daily activities and exercises. Check the videos about how to perform the activities.
- 5. Check monitoring data measured with the delivered clinical devices: scale, blood pressure and activity tracker.
- 6. Medication: register medications and when to take them. Confirm that you have taken the medications. Register spontaneously taken medicines.
- 7. Statistics: check your values in the statistics (at the end of the testing period).
- 8. Health literacy: check the knowledge modules and the knowledge tests that you can perform.

We invited the test users to record any problems they encountered while they were using the system and report it to the members of the project team

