#### 3.2.6 Usability questionnaire

We invited the users to answer a questionnaire with statements regarding the usability of the SENACA system. They were asked to evaluate different devices and functions on scale from 0 to 5. The result is presented in table 8.

		0	1	2	3	4	5	
Learning to use the system	Difficult					2	4	Easy
Navigate	Difficult				1	4	1	Easy
Readability of content	Difficult				1	4	1	Easy
Few steps as possible	Disagree	1			1	4	1	Agree
Error messages	Unhelpful				2	1	3	Helpful
Graphical presentation	Confusing					2	5	Very clear
Easy to use: Monitoring	Disagree					1	6	Agree
Easy to use: Medication	Disagree					3	3	Agree
Easy to use: Nutrition	Disagree			1	2	2	1	Agree
Easy to use: Activity	Disagree				1	1	4	Agree
Easy to use: Health literacy	Disagree	1				3	1	Agree
Easy to use; blood pressure device	Disagree						7	Agree
Easy to use: Scale	Disagree						7	Agree
Easy to use: Activity tracker	Disagree				2	2	3	Agree

Table 8. Result from usability questionnaire in Norway and Switzerland (n=7).
Overall, the numbers from the questionnaire show that the test users are quite or very satisfied with the system. Looking at all the functionalities, we see that majority of the test users give them a positive score, 3-5, and for many of the functionalities we see that a majority of the test users give them a score of 4 or 5. If we look at the statements regarding usability of the system as a whole, statement 1 to 7, we see that the majority of the test users are satisfied with the system.

When we look at the statements regarding the five basic functions that the system offers (monitoring, medication, nutrition, activity, and health literacy) we see some differences. Although a majority say it is quite or very easy to use these functionalities, we see that there are one person who mark the statement regarding usability of the Nutrition module with 2 and one person who mark the statement with 1. We also see that the function Nutrition do not have as many top scores as the other functions, except for Health literacy. Although the users found it quite easy to use the Health literacy module, except for one of the users, we see that only five persons have answered the questions regarding Health literacy.

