The test users have not encountered many errors, and many of them have not seen an error messages. However, several users have encountered one specific error. Sometimes during the test period, they have experienced that data from the scale has not been transmitted to the web-platform. Normally they would just use the scale one more time. One of the users reported that he/she only experienced errors a couple of times with the scale and he/she found the error messages to be helpful (NO). One of the Swiss users said that activity tracker sometimes did not transmit all the data, and there was no error messages (SW). This is something that Norwegian also have experienced but they have noticed that the data have been transmitted later.

The users found the graphical presentation to be adequate and made it quite easy to find and activate the relevant modules.

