#### 3.3.2 Usability of the modules

The SENACA web-platform offers the users to activate different modules. Many of the users were commenting on the Nutrition module. Before you activate the module, you have to answer a set of question regarding your food intake. One of the users found that going through the questionnaire and registering the daily intake of three items was too time-consuming, and there were this problem of remembering past nutrition (SW). Another user would like to have a module where he/she could register all the food he/she has been consuming during the day and not just the three items he/she was to focus especially on (NO). A third user was asking about the possibility of administering the data regarding nutrition when he/she had forgot to register the nutrition. He/she felt it is demotivating when you get a message on the dashboard telling that you have not completed a task.

Medication is module that the users have not used so often, maybe because many of the users do not use medicine. One of the users, who is using medicine, said that is was of no relevance since he/she uses a medical dispenser (SW). Another user, who have tried the medication module but only using fake data, said that system kept reminding the user when he/she had forgotten to take the medicine even though he/she could not just take extra medicine the day after (NO). One solution would be just to register that you have taken medicine, but then the data regarding medicine adherence is not correct.

The users found it easy to use the activity tracker module. One of the users commented on checking the SENACA website in the morning. He/she said that when h/she accesses the website in the morning you get a "Caution" about physical activity while he/she hardly had started the day (NO). Is it possible to show the results from the activity tracker from the day before, he/she asked?

The test users have tested the blood pressure device on a more or less regular basis. They all said it was easy to use the module. However, two of the users were commenting on the blood pressure statistics and thought that data of the blood pressure (systolic and diastolic) should be presented in one table and not in two tables (NO).

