#### It is easy to use the activity tracker.

Disagree	0	1	2	3	4	5	Agree
----------	---	---	---	---	---	---	-------

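### PSSUQ items 9 and 10 ask for a rating even from users who saw no error message or made no mistake, so a score on them can mean an opinion or no experience at all

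*Protocol*

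**What the plan says.** **Main study.** Table 4 names the PSSUQ as the measure of user satisfaction, and Table 6 schedules user satisfaction at days 50 and 100. Annex 2b prints 18 statements on a scale from -3 to +3 with the instruction "Remember to select a single option for each statement". Item 9 is "The system gave error messages that clearly told me how to fix problems"; item 10 asks how easily and quickly the user recovered after a mistake. No 'not applicable' option is printed. Annex 6 does print one, for the Vitalograph and the glucose device. Section 2.2.4 counts easy recovery as part of the usability construct 'errors'.

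**Pre-test.** Seven users in Norway and Switzerland completed the Annex 12 questionnaire, scored 0 to 5, with results in Table 8. Six scored error messages: two gave 3, one gave 4 and three gave 5. Section 3.3.1 says of the same users that "many of them have not seen an error messages", and reports one user who had seen such messages and found them helpful.

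**Annex 12 as printed.** "It is easy to use the activity tracker" appears twice: once between the Monitoring and Nutrition modules, and again at the end. There is no item for the Medication module, although Table 8 reports one between Monitoring and Nutrition. Section 3.2.4 describes the Israeli test as still under way.

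**The concern.** Items 9 and 10 are conditional: they make sense only to someone who saw an error message or made a mistake. Without a way to say that this did not happen, the form gathers two kinds of answer under one number and they cannot be separated afterwards. A neutral tick from a user with no errors pulls a poor rating from affected users towards the middle. A favourable tick, given because nothing went wrong, makes error handling look good on no evidence. The direction of the distortion is therefore unknown.

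These two PSSUQ items are where a participant rates how well errors are explained and how easily mistakes are put right. The study exists to find features to improve, and a prototype's error handling is an obvious candidate. The Annex 12 misprint is a smaller matter of the same kind: used as printed, the form would yield two activity tracker ratings and no Medication rating.

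**Working it through.** No sample-size or power calculation is involved. The check uses the Table 8 counts and the text of sections 3.2 and 3.3.

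**1. Reproduce the pre-test sample.** Answers per row in Table 8, in printed order: 6, 6, 6, 7, 6, 7, 7, 6, 6, 6, 5, 7, 7, 7. No row exceeds 7, which agrees with n = 7, and the Health literacy row sums to 5, as the text says. The total is 89 of 14 x 7 = 98 cells, so 9 cells are blank, spread over 8 of the 14 rows.

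**2. Error-message row.** Answers: 2 + 1 + 3 = 6 of 7. Mean: (2x3 + 1x4 + 3x5)/6 = 25/6 = 4.17.

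**3. How many of those six scores came from users who saw no message?** Let k be the number of the 7 who saw none. The number who both saw none and gave a score is at least k + 6 - 7 = k - 1. The document says only 'many', so k is an assumption. I take 2 as the lower limit, and 6 as the upper limit because at least one user did see messages.

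| k (assumed) | Scores from unexposed users, at least |
|---|---|
| 2 | 1 |
| 3 | 2 |
| 4 | 3 |
| 5 | 4 |
| 6 | 5 |

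**4. What could the mean among exposed users be?** The six scores are 3, 3, 4, 5, 5, 5. Which belong to unexposed users is unknown, so take the extremes after removing m of them.

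| m removed | Lowest mean | Highest mean |
|---|---|---|
| 1 | 20/5 = 4.00 | 22/5 = 4.40 |
| 2 | 15/4 = 3.75 | 19/4 = 4.75 |
| 3 | 10/3 = 3.33 | 15/3 = 5.00 |
| 4 | 6/2 = 3.00 | 10/2 = 5.00 |
| 5 | 3.00 | 5.00 |

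The reported 4.17 is thus compatible with anything from 3.0 to 5.0 among users who had the experience.

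**5. Reach within the PSSUQ.** Items 9 and 10 are 2/18 = 11% of the items.

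- *On one of these items:* reported mean = (1 - p) x mean among exposed + p x mean among unexposed, where p is the unexposed share. As an illustration with assumed values, a mean of -2 among the exposed and 0 from the unexposed gives -1.5, -1.0 or -0.5 for p = 0.25, 0.50 or 0.75.
- *On one unexposed user's 18-item mean:* let the other 16 items average M and let the user tick 0 on both. The 18-item mean is 16M/18, which differs from M by 2M/18. Since M lies between -3 and +3, the shift is at most 6/18 = 0.33.

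The effect on the item can be large. The effect on the overall score is modest.

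**6. Annex 12 against Table 8.** Annex 12 prints 15 items, the number given in section 3.2.1. Replacing the first activity tracker item with Medication gives exactly the 14 rows of Table 8 plus the setup item.

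**The case against.** Several arguments weigh against this point, and some of them hold.

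- *The pre-test did not use the PSSUQ.* Correct. It shows that people will score an error-message item without exposure, but on another form, with another scale and no instruction to answer every statement. It lasted 10 to 21 days against up to 100 in the study, so main-study users have more chance to meet an error. It says nothing about item 10.
- *The study records errors elsewhere.* Table 4 lists self-reported and automatically recorded errors, and Annex 6 asks about problems over the last 50 days. These help, but they capture technical problems. They do not show whether a message was displayed or whether the user made a mistake. Section 3.3.1 gives an example: tracker data failed to arrive and no message appeared.
- *Scoring belongs in an SAP.* The scoring rule may. The answer options cannot, because an analysis plan cannot recover exposure that the form never asked about.
- *The analysis is descriptive.* True: "Explorative and descriptive data analyses will mainly be performed in this field-test study with a relatively small sample size". That limits the consequence, but a descriptive item result still has to say whose experience it describes.

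A reader might also infer more than the documents allow:

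- *That Annex 12 forces a score.* It carries no such instruction, and 9 of 98 cells were left blank. It merely lacks the option.
- *That the Medication ratings come from non-users.* The text says "Medication is module that the users have not used so often, maybe because many of the users do not use medicine". Rare use is not absence of use, section 3.2.5 invited everyone to try the module, and the user who entered made-up data did operate it.
- *That the setup item distorted a result.* Project partners did the registration and device configuration, and of those tasks section 3.2.5 says "These tasks have not been tested by the test users". But Table 8 has no setup row, so no reported result is affected.

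**Conclusion.** The point holds for PSSUQ items 9 and 10. As printed, they collect a number from participants with nothing to rate, and 0 cannot be told apart from 'did not occur'. The pre-test makes this a realistic worry for error messages: for any k of 2 or more, at least one of the six scores came from a user who had seen none, and the mean among exposed users is not determined within 3.0 to 5.0. This rests on two assumptions: a range for k that the document does not give, and that the statement in section 3.3.1 describes the whole test period.

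The reach is 2 of 18 PSSUQ items and one Table 8 row. It would be wrong to conclude that the usability ratings as a whole fail to measure experience. The other 16 PSSUQ items are not affected by this defect, and ratings such as those for the scale and the blood pressure device (7 of 7 each) stand. The overall pre-test conclusion in section 3.4 does not cite the error-message rating. The Annex 12 misprint is a separate, minor slip, and it matters only if the printed form is used again.

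**What to change.** 1. In Annex 2b, add 'not applicable / did not occur' to items 9 and 10. Add the same box to the error-message item in Annex 12.
2. Score the PSSUQ as the mean of answered items, and report items 9 and 10 with the number of users who had the experience.
3. In section 3.3, note that the error-message row of Table 8 probably includes users who saw no error message. No such note is warranted for Medication.
4. Before the Israeli test, replace the first of the two activity tracker items in Annex 12 with the Medication module item that Table 8 reports.

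The cost is a tick box on three items, one corrected item, a scoring sentence and a note in the text. The downside is fewer answers on the conditional items, but those that remain will come from users with something to rate.
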